#### 5.4 Secondary outcomes measure(s)

- proportion of participants choosing each of the study interventions, with reasons for their choices
- proportion of participants who switch treatments, with reasons for switch
- treatment fidelity
- loss to follow-up rates over 12 months
- efficacy outcome estimates after 6 months' of follow up, post treatment, to inform outcome measure instruments' responsiveness (minimum important difference, MID)

# 6 Study design and setting

#### PROSPECTIVE COHORT STUDY (0 to 36 months)

The setting is secondary care, including dermatology departments, plastic and general surgery departments, and HS multi-disciplinary clinics. Community recruitment is also planned because of the average seven-year delay before HS diagnosis (13) and based on the experience of successful recruitment using community advertising for the NIHR-funded Hi-Light study in vitiligo (14) - another condition that is often neglected by health services. 150 participants will be recruited.

Participants will be asked to select one of the treatment options detailed in section 4.1 that is appropriate for their care. The clinician will advise the participant on which treatments are most suitable and available to help guide their treatment choice. If a site is unable to offer the chosen treatment, it may be possible for the participant to attend a neighbouring hospital site to receive that treatment, subject to local arrangements. If on discussion with their clinician the participant prefers another treatment outside of the study treatments being offered by the recruiting site they will not be recruited and their reason(s) for preferring another intervention will be recorded in the screening log. No randomisation is necessary for this prospective cohort study. If the participant's first choice is an intervention for which the waiting time at their centre is a significant time, they will be offered treatment to cover the interim period based on the joint decision between the clinician and the participant. The interim treatment would preferably be one of the study interventions, however, other treatments are permitted depending on clinician judgement. Participants will be allocated to their chosen treatment interventions and followed-up for a period of up to 12 months. The clinical effectiveness outcomes will be assessed at 6 months following the time the patient made their intervention choice. Once the participant has been on the chosen intervention for 6 months they will be free to choose alternative treatment options or combinations of treatments as required. Followup will be continued for up to a further 6 months.

No formal training will be provided for conventional surgical options, as the objective of the cohort study is to document variability in current practice. The surgical technique used for each procedure will be carefully documented and some basic parameters will be included in a protocol which allows for wide variation in practice. Choice of laser for hair removal treatment will be dictated by the participant's skin type and the laser(s) available at the recruiting centre.

The deroofing intervention is not currently offered as standard treatment in the UK. In keeping with the Ideal stage 2b framework, a bespoke training package will accelerate surgical innovation by fast-

tracking the application of surgeons' existing skills. An in-person training session between the potential early adopters (surgeons recruiting into the study) and innovators (a UK deroofing expert) will take place at the beginning of the THESEUS study (11). The training materials will be made available on the Reconstructive Surgery Studies Network website, so that surgeons who were not available to attend can still access the training.

Feedback on the training event will be sought from attendees, so that it can be modified and then reused before a definitive study. The edited videos of procedures can be used more widely to support the diffusion of innovation as part of the outputs of the proposed project. Continuing Professional Development points will be sought from the Royal College of Surgeons of England for those undergoing the training.

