Hair removal is performed by individuals trained and certified in the use of medical lasers (clinicians or NVQ level 3 certified individuals), and it is believed that only limited use in people with HS in the UK may be due to underuse of referral pathways to allow patients to access laser treatment. Training in laser treatment is already formalised as part of medical laser training. Certification is required for individuals to be insurable. Providing formal training in laser treatment within this project is not necessary, however a laser protocol will be provided.

Deroofing uses standard surgical equipment and transferable skills that will already be possessed by surgeons and some dermatologists (10). However, there is limited awareness of the technique in the UK, which is likely to account for its low uptake.

Each study site will offer at least 4 of the 5 interventions.

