#### 5.3 Primary outcomes measure(s)

Proportion of participants who are eligible, and hypothetically willing, to use the different treatment options.

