#### 8.1 Inclusion criteria

- Adults at least 18 years old with active HS of any severity
- Diagnosis meets disease definition (a lifetime history of at least 5 flexural skin boils or 2 flexural skin boils in last 6 months) and confirmed by recruiting clinician with experience of HS care
- HS not adequately controlled by current treatment
- At least one of the five study interventions is appropriate for participant's care

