#### 9.2 Screening logs

A screening log of all ineligible and eligible but not consented/not approached patients will be kept at each site so that any biases from differential recruitment will be detected. These screening logs will

contain patient identifiers, for example, patient initials and/or date of birth. The screening log should be sent to the THESEUS study email address every month.

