#### 9.4 Informed consent

Please refer to section 9.1 for participant identification and recruitment processes. Where the recruitment appointment is face-face, consent will be taken by suitably qualified PIs, co-investigators and research nurses. Participants will receive the current version of the Participant Information Sheet (PIS) prior to the consent process and will be given plenty of time to ask questions relating to the PIS and other elements of the study prior to consent being taken. Where the recruitment appointment is conducted remotely, the participant will be sent the PIS and consent forms (carbon triplicate copies) via post or email. One copy of the signed consent form will be kept by the participant and the other copies returned to the research site and the CTR. Participant care will remain paramount at all times. Specific consent will be requested from participants to be involved in the interview component of the study (See section 13.1.2 for consenting process). Interviews with participants will be carried out by researchers based at Nottingham University. Consent for these elements is not required in order to participate in the cohort study (ie. taking part in an interview is optional). Participants who are invited to attend the consensus workshop will not be asked formally for their consent, as their attendance

Consent will be sought to contact participants at the end of the study regarding opportunities to participate in future HS research studies.

will provide implied consent. Participants who are invited to attend the workshop may or may not

Informed consent will be obtained prior to the participant undergoing procedures that are specifically for the purposes of the study. Only when written informed consent has been obtained from the participant and they have been enrolled into the study will they be considered a study participant.

We will comply with Welsh language requirements and the PIS, Consent Form and any other required participant documentation will be available in Welsh. However, all documentation used for data collection (i.e. outcome measures) will remain in English as they are designed and validated in English.

have taken part in the interview component of the study.

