#### 15.5 Inclusion in analysis

All enrolled participants will be included in the analysis. In the event of withdrawals, data up to the point of withdrawal of consent will be used.

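### Willingness and uptake are measured only in enrolled participants, so both are conditional on accepting the treatments a site offers, and the bias can run either way by option

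*Protocol*

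**What the plan says.** - **Primary outcome (Section 5.3):** "Proportion of participants who are eligible, and hypothetically willing, to use the different treatment options".
- **Uptake outcome (Section 5.4):** "proportion of participants choosing each of the study interventions, with reasons for their choices".
- **Who is a participant (Section 9.4):** only when written consent has been given and "they have been enrolled into the study will they be considered a study participant". Section 15.5 adds: "All enrolled participants will be included in the analysis". No one outside the enrolled cohort enters either proportion.
- **Entry:** Section 8.1 requires that "At least one of the five study interventions is appropriate for participant's care". Section 6 adds that a patient who, on discussion, "prefers another treatment outside of the study treatments being offered by the recruiting site they will not be recruited"; the reason goes into the screening log. Under Section 9.5.1 every person registered chooses one of the five interventions.
- **Availability (Section 4.1):** "Each study site will offer at least 4 of the 5 interventions". Sections 6 and 11 say that someone whose chosen treatment is not offered locally may be able to attend a neighbouring site, subject to local arrangements.
- **Screening log (Section 9.2):** "A screening log of all ineligible and eligible but not consented/not approached patients will be kept at each site", with the stated purpose of detecting bias from differential recruitment.
- **Sample size (Section 15.1):** the least favoured option in the patient survey, minor surgical operations including deroofing, had 13%; 150 patients are expected to yield 20 choosing it.
- **Main analysis (Section 16.1):** willingness is described overall and by stated preference and uptake, with intra-cluster correlation by centre. Neither the log nor site availability is mentioned.

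**The concern.** The study exists to inform future randomised trials, and recruitment feasibility is a named secondary objective (Section 5.2). The population of interest for that purpose includes eligible patients who were turned away because they wanted something else. Entry to the cohort depends partly on treatment preference, which is close to what the outcomes measure, so the enrolled-only proportions describe patients who accepted what their site could provide.

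Two kinds of lost patient matter, and they act differently:

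1. A patient who wants a treatment outside the five is not enrolled. If such patients are less willing than enrolled ones to use the study options, the enrolled-only willingness figures are too high.
2. A patient who wants one of the five that the site does not offer is not enrolled, is sent to another site, or settles for a different option. Unless the patient is successfully sent on, uptake of the wanted option is too low and uptake of others too high. Willingness for the wanted option also falls if the patient is not enrolled.

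Pooled uptake therefore mixes preference with local supply. A future trial team could misjudge demand for an option, and the count expected in Section 15.1 for the IDEAL 2b evaluation makes no allowance for availability.

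**Working it through.** **Step 1. The plan's own figure.** Expected number choosing the least favoured option: 0.13 × 150 = 19.5, stated as 20. It reproduces, but only if the option is reachable for every recruit.

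**Step 2. Uptake when some sites lack the option.** Let f be the share of patients at sites without the option and r the share of those wanting it there who are referred on and enrolled. The protocol gives neither, so both are assumed. The share lost is l = f(1 − r).

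- If the lost patients are not recruited, they leave numerator and denominator: observed = 0.13(1 − l) / (1 − 0.13 l).
- If they enrol and choose something else, they leave only the numerator: observed = 0.13(1 − l).

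For f = 20%, r = 0: 0.13 × 0.8 / (1 − 0.13 × 0.2) = 0.104 / 0.974 = 10.7%, against 0.13 × 0.8 = 10.4%.

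| f (assumed) | Not recruited, r = 0 | Not recruited, r = 50% | Choose something else, r = 0 |
|---|---|---|---|
| 10% | 11.9% (17.8 of 150) | 12.4% (18.6) | 11.7% (17.6) |
| 20% | 10.7% (16.0) | 11.9% (17.8) | 10.4% (15.6) |
| 50% | 7.0% (10.4) | 10.1% (15.1) | 6.5% (9.8) |

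Other options move the opposite way. An option offered everywhere with a true 30% share reads 0.30 / (1 − 0.13 × 0.2) = 30.8% at f = 20%, r = 0, when the lost patients are not recruited.

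**Step 3. Willingness for one option.** Assume 60% of 150 enrolled are willing (90 people), t otherwise eligible patients are logged as not recruited for preference, and k of them are willing for that option. On the wider denominator the proportion is (90 + k) / (150 + t).

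- k = 0: 90/165 = 54.5% (t = 15), 90/180 = 50.0% (t = 30), 90/200 = 45.0% (t = 50).
- t = 30, k = 10: 100/180 = 55.6%.
- t = 30, k = 18 (as willing as those enrolled): 108/180 = 60.0%, no bias.
- t = 30, k = 30 (all wanted this option): 120/180 = 66.7%, so the enrolled-only 60% is too low.

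The sign therefore depends on what the lost patients wanted.

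**Step 4. Yardstick.** The 95% half-width at n = 150 is 1.96 × √(0.6 × 0.4 / 150) = 7.8 points at 60%, and 8.0 points at 50%. Section 15.1 states 7 points, which needs a proportion near 0.26 or 0.74 that it does not give. Section 15.1 also concerns willingness to be randomised, so it serves here only as a scale. The shifts in Step 3 range from none to 15 points and can be smaller or larger than sampling error.

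**The case against.** The strongest reply is that the protocol foresaw this. Reasons for preferring another treatment are logged, the log's declared purpose is to detect recruitment bias, reasons for choice are an outcome, eligibility for each intervention is recorded at baseline, and centre clustering is estimated. Where the log counts are tabulated could be left to the SAP. This stands in part: most of the data needed are planned. But the protocol itself fixes the denominator and the entry rule, and its main analysis never brings the log or site availability into either outcome. An intra-cluster correlation would absorb differences in what sites offer without separating them from preference.

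A second reply is that the exclusion sentence may cover only treatments outside the five, since the neighbouring-site sentence comes shortly before it. That is a fair reading. Under it the second kind of loss is smaller, although the clinician still steers choice towards what is available. The two sentences can be read against each other and need reconciling.

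Three stronger readings are tempting, and the documents do not support them:

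- **That willingness is inflated across the board.** The outcome is per option, and an enrolled patient may be unwilling to use the other four. Only willingness to use at least one option is close to 100% by construction, and that is not the stated outcome.
- **That uptake of deroofing and laser is known to be understated.** Their rarity in Section 4.1 describes UK practice. Nothing says which intervention any study site will lack, and the study provides deroofing training.
- **That everyone turned away was unwilling.** Preferring something else is not unwillingness, and counting a patient who wanted an unavailable study option as unwilling for it would depress that option further.

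**Conclusion.** The point holds in a limited form. The willingness and uptake proportions are conditional on accepting the treatments a site offers, and no stated analysis relates them to the patients turned away or to site availability. The direction differs by option, and the size cannot be derived from the protocol, which gives no availability, referral or turn-away rates. For a true preference of 13%, the assumed ranges above give an observed uptake of 6.5% to 12.4%, or about 10 to 19 of 150 patients against the planned 20. The central illustration (20% of patients at sites lacking the option, no referral) gives 10.4% to 10.7%, about 16 patients. If every site can supply or arrange every option and those turned away are as willing as those enrolled, there is no bias. This is an inexpensive improvement in reporting and does not invalidate the design.

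**What to change.** 1. **Section 6:** reconcile the neighbouring-site sentence with the exclusion sentence, so that it is clear whether a patient wanting one of the five interventions that is not offered locally is recruited.
2. **Screening log (Section 9.2):** code the preferred treatment, naming the study intervention or recording non-study treatment. Noting any reason the patient was ineligible for the named option would help, because baseline eligibility is recorded only for enrolled participants.
3. **Uptake (Sections 5.4 and 16.1):** report each intervention among participants at sites offering it, alongside the pooled figure.
4. **Willingness (Sections 5.3 and 16.1):** report each option also on enrolled participants plus otherwise eligible patients logged as not recruited for treatment preference. Count those who wanted a named study option as willing for that option, and treat the rest as unwilling, to give a lower bound.
5. **Reporting:** describe the enrolled-only figures as conditional on accepting the treatments offered.

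The cost is one coded log field, a record of what each site offers, some analysis wording and an extra table. The drawback is that log data are less complete than cohort data, so item 4 is a sensitivity bound and not a point estimate.

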# 2 Synopsis

Short title	Treatment of Hidradenitis Suppurativa Evaluation Study
Acronym	THESEUS
Internal ref. no.	
Development phase	N/A
Funder and ref.	NIHR HTA (ref 17/98/01)
Study design	Prospective observational cohort study
Study participants	Adults with active Hidradenitis Suppurativa (HS) of any severity
Planned sample size	150
Planned number of sites	10 secondary care sites
Inclusion criteria	
 
Adults at least 18 years old with active HS of any severity
 
Diagnosis meets disease definition (a lifetime history of at least 5 flexural skin boils or 2 flexural skin boils in last 6 months) and confirmed by recruiting clinician with experience of HS care
 
HS not adequately controlled by current treatment
 
At least one of the five study interventions is appropriate for participant's care
 

Exclusion criteria	
 
Unable or unwilling to give informed consent
 
Pregnancy or breastfeeding
 
Not fluent in English (questionnaires are only validated in English)
 

Treatment duration	Up to 6 months
Follow-up duration	12 months
Planned study period	36 months
Primary objective	To inform the design of future HS RCTs and to understand how HS treatments are currently used
Secondary objectives	To determine i) feasibility of recruitment for future RCTs of HS treatments; ii) choice and characterisation of study interventions (dose of medication, type of surgical techniques used); iii) current patient pathways and understanding of what influences patients' and clinicians' treatment choices; iv) choice, feasibility and responsiveness of outcome measure instruments, including evaluation of minimum important difference (MID) to inform sample size calculations; and v) consensus-agreed recommendations for future study designs
Tertiary/Exploratory objectives	N/A
Primary outcomes	Proportion of participants who are eligible, and hypothetically willing, to use the different treatment options

Secondary outcomes	
 
proportion of participants choosing each of the study interventions, with reasons for their choices
 
proportion of participants who switch treatments during the study follow-up period, with reasons for switch
 
treatment fidelity
 
loss to follow-up rates over 12 months
 
efficacy outcome estimates after 6 months' of follow up to inform outcome measure instruments' responsiveness (minimum important difference, MID)
 

Tertiary/Exploratory outcomes	N/A

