# **10 Study Intervention**

#### 10.1 Specified interventions

- i) Oral doxycycline 200mg OD for 6 months, with the option to continue for up to a further 6 months or switch to another intervention or combination of interventions after the participant has been on their chosen intervention for 6 months;
- (ii) oral clindamycin and rifampicin both 300mg BD as a combined course for 10 weeks, with the option to continue up to 6 months and thereafter switch to another intervention or combination of interventions after the participant has been on their chosen intervention for 6 months;
- (iii) laser treatment using nd-YAG laser (skin types 2-6) or Alexandrite/ diode laser (skin types 1-3) administered on 4 occasions each one month apart, with the option to receive another intervention or combination of interventions 6 months after the first laser treatment and for up to a further 6 months;

- (iv) deroofing of sinus tracts using electro-cautery (optimal protocol to be determined by UK expert and provided to centres as a training package including a video). It is expected that by following this training video that healthcare professionals, including; dermatologists, plastic surgeons and other surgeons will be able to perform this procedural intervention. The procedure is carried out under local anaesthetic. , repeated during the next 6 months if necessary and with the option to receive another intervention or combination of interventions 6 months after the initial deroofing treatment and for up to a further 6 months. The total area treated at one time is limited by the volume of local anaesthetic needed and expected degree of impairment of activities of daily living during recovery;
- (v) conventional surgery (narrow or wide excision, with a range of closure methods depending on the preference of the clinician), with the option to receive another intervention or combination of interventions 6 months after the surgery and for up to a further 6 months.

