# 11 Study procedures

The duration of participant involvement in most cases will be up to 12 months. Efficacy of interventions will be assessed at 6 months following their baseline appointment (when they make their intervention choice) and then participants are free to switch to another intervention or combination of interventions after the participant has been on their chosen intervention for 6 months. Participants who opt for an intervention that has a significant delay before receipt of that intervention can opt to have another intervention during that wait time. If a site is unable to offer the intervention chosen by the patient, it may be possible for them to attend a neighbouring study site, subject to local arrangements. Some participants will attend the consensus workshop that will take place at a point during the final year of the study.

Study assessments will entail a clinical history, completion of questionnaires and a clinical examination. These assessments will take place at baseline and every 3 months following baseline up to 12 months post baseline (see figure 1).

We will collect information about potential confounders including body site, baseline disease severity (measured by Hurley staging) (12), previous treatment received, smoking and body mass index. We will also record if participants are referred to additional services to support the management of HS (e.g. weight-loss, smoking cessation and psychological resilience programmes).

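### The 6-month efficacy outcome has two time origins, after treatment and after the choice of treatment; with a wait for a procedure, the month-6 change can be mislabelled as its efficacy

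*Protocol*

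**What the plan says.** Four places in the protocol time the efficacy outcome.

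- Section 6 (Study design and setting): "The clinical effectiveness outcomes will be assessed at 6 months following the time the patient made their intervention choice".
- Section 11 (Study procedures): "Efficacy of interventions will be assessed at 6 months following their baseline appointment (when they make their intervention choice").
- Section 5.4 (Secondary outcomes): "efficacy outcome estimates after 6 months' of follow up, post treatment, to inform outcome measure instruments' responsiveness".
- Section 2 (Synopsis), same outcome: "efficacy outcome estimates after 6 months' of follow up to inform outcome measure instruments' responsiveness". The words that place the clock after treatment are absent.

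The protocol expects that treatment may not start at the time of choice. Section 6 covers a participant who opts for "an intervention for which the waiting time at their centre is a significant time, they will be offered treatment to cover the interim period". That cover would preferably be a study intervention, but "other treatments are permitted depending on clinician judgement". Section 11 repeats the point: "Participants who opt for an intervention that has a significant delay before receipt of that intervention can opt to have another intervention" while waiting. No expected or maximum wait is given, and no rule moves the efficacy assessment when treatment is late.

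Reviews are at baseline and at months 3, 6, 9 and 12, counted from baseline (section 11 and Figure 1). The intervention received is recorded at each of them. Section 16.1 plans the average change over time in each efficacy outcome, by group, with 95% confidence intervals. It does not say there whether the group is the one chosen or the one received.

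**The concern.** Six months after treatment and six months after choice are the same moment only for someone treated on the day of choosing. That is nearly so for a course of tablets. It need not be so for surgery, deroofing or laser, where a waiting list is the situation that sections 6 and 11 describe.

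If the choice-based clock is used, participants in a group with a wait reach month 6 with less time since treatment than those in a group without one, and some may not have been treated at all. Their change from baseline then mixes the wait, any interim treatment and the early course after the procedure. Section 11 nevertheless calls the month-6 result efficacy of the interventions. A reader of the per-group changes would take them as comparable in timing, which they are not. Section 12.1 also classes withdrawals from intervention by whether they fall before the 6-month efficacy time point, so that category inherits the same ambiguity.

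**Working it through.** The plan states no figure on this point, so there is nothing to reproduce. The check is timeline arithmetic.

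**Inputs.** Efficacy visit at month 6 after choice (sections 6 and 11). Reviews at months 0, 3, 6, 9 and 12 (section 11). Laser is "administered on 4 occasions each one month apart" (section 10.1), so the fourth session falls 3 × 1 = 3 months after the first. The wait w, in months from choice to first receipt of the chosen intervention, is an assumption, taken from 0 to 7 because the protocol gives none.

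**Formulas.** Months since surgery or first deroofing at the month-6 visit = 6 − w. Months since the fourth laser session = 6 − (w + 3). Study month at which 6 months after treatment start is reached = 6 + w.

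| w | Since surgery or deroofing at month 6 | Since fourth laser session at month 6 | 6 months after start falls at month |
|---|---|---|---|
| 0 | 6 | 3 | 6 |
| 1 | 5 | 2 | 7 |
| 2 | 4 | 1 | 8 |
| 3 | 3 | 0 (fourth session just due) | 9 |
| 4 | 2 | 1 month of course left | 10 |
| 5 | 1 | 2 months of course left | 11 |
| 6 | 0 (day of procedure) | 3 months left (first session due) | 12 |
| 7 | not yet done | not yet begun | 13, after the last review |

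**Dilution.** Let f be the share of a group still untreated at month 6. If interim treatment had no effect and the treated had their full change (both assumptions), the group mean would be (1 − f) of the true change: 90%, 75% or 50% for f = 10%, 25% or 50%. Section 15.1 expects about 20 participants for deroofing (13% of 150 = 19.5). In a group of 20, those shares leave 18, 15 or 10 treated. The documents support no particular f. An effective interim treatment would shrink this dilution or even reverse it.

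**Can the existing reviews serve a treatment-based clock?** For w from 0 to 6 the target month 6 + w lies between 6 and 12. Reviews are 3 months apart there, so the nearest is at most 1.5 months away. For w above 6 the target lies past month 12, and no 6-month post-treatment value exists.

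**What that clock costs.** Suppose the starting value is the last review before treatment and the end value is the review nearest the target. At w = 1 the target is month 7, the nearest review is month 6, and the change runs from month 0 to 6, a 6-month interval. At w = 2 the target is month 8, the nearest review is month 9, and the change runs from month 0 to 9, a 9-month interval. The intervals are therefore unequal. At w = 4 or 5 the starting value is the month-3 review, which may be taken on interim treatment.

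**The case against.** The strongest defence is that the choice-based clock is deliberate. Sections 6 and 11 state it alike, and section 11 explains that baseline is when the choice is made. This is an observational cohort meant to describe current use and patient pathways, and waits are part of that. Outcome from the decision is a legitimate target and avoids selecting those who reach the procedure. That stands. What it does not rescue is the efficacy label in section 11 or the wording of section 5.4.

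It can also be said that the SAP, which is not at hand, may settle the matter, and that the data to do so are largely planned: intervention received at every review, a surgeon form after each operation, and daily pain texts that begin with treatment. That makes repair easy. It does not remove a conflict between two statements in the protocol itself.

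A reader might infer more than the documents support:

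- *That section 10.1 is a third conflicting efficacy clock.* It counts 6 months from first laser, first deroofing or surgery, but to say when another intervention may be received. It sets no efficacy assessment time.
- *That interim-drug response will be credited to procedures.* This requires groups defined by choice and use of month 6 alone. Section 16.1 fixes neither in its sentence on change over time.
- *That effect sizes for future trials will be wrong.* The stated purpose of these estimates is instrument responsiveness and the MID. No comparison between interventions is planned.
- *That the MID is invalid.* The anchor method needs instrument and anchor measured over the same interval, not a common treatment clock.

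**Conclusion.** The contradiction is real. Section 5.4 times the secondary efficacy outcome from treatment, sections 6 and 11 time it from choice, and the synopsis leaves it open, while the protocol itself foresees waits that separate the two. For a wait of w months the month-6 value carries 6 − w months of the chosen treatment, and none once w reaches 6. The per-group change is therefore not on a common treatment clock and can be mislabelled as efficacy of the procedure.

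The timeline follows from the protocol's own schedule. How often it matters cannot be sized, because no waiting times are given; the dilution percentages show scale only under the stated assumptions.

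The reach is limited. The primary outcome, eligibility and hypothetical willingness, is untouched. The anchor-based MID and minimal important change are affected less than the per-intervention changes. This is a defect of definition and labelling in a secondary outcome, and worth correcting because the correction is cheap.

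**What to change.** 1. Reconcile the synopsis and sections 5.4, 6 and 11 on one stated time origin for the efficacy outcome.
2. Label the result at month 6 after choice, by chosen group, as the outcome of choosing that pathway. Report beside it, for each group, the number not yet treated and the distribution of time since treatment start.
3. Record the start date of the chosen intervention separately from the start of any interim treatment.
4. Add, under its own label, a per-intervention efficacy estimate timed from first receipt of the chosen intervention. Use the existing 3-monthly reviews with the actual elapsed time, and describe interim treatment and later switches.

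The cost is wording and, if not already captured, one date field; no visits are added and no treatment rule changes. The added estimate has clear limits: fewer participants in the procedure groups, with no 6-month post-treatment value for waits over about 6 months; pre-treatment values possibly taken on interim treatment; unequal intervals; and selection of those who received the procedure. For these reasons it should stand beside the pathway result and not replace it.
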